### Recruitment Process

A series of health screening camp were organised around Kulai district located in the south of Malaysia. Johor state was specifically selected due to high prevalence of MetS as reported in Malaysia Adults Nutrition Survey (MANS) (11) (12), Metabolic Syndrome Study Malaysia (MSSM) (13) and National Health and Morbidity Survey 2015 (NHMS) (14). The eligibility screening and recruitment of study participants were conducted in four low to middle income neighbourhoods. The research team provide assistance on identifying potential study participants according to the eligibility criteria (Table 1). If an individual is found to eligible to participate, they will be requested to complete the baseline questionnaire after consenting for their participation.

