### Randomisation and Treatment Allocation

Eligible adults who have consented to participate are matched for age, sex and ethnicity as baseline. To minimised contamination, participants were randomised to either intervention or control group based on their location.

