## Randomisation and Blinding

This study is an open label parallel randomized-controlled trial hence both the research team and participants will not be blinded. However, as the randomisation will be made based on participants location, contamination of participants was minimised.

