### Applicability in Low-to-middle Income Population

The RCT of PERSUADE will be conducted in four low-to-middle class neighbourhoods in Johor which means the participants may be of a lower socioeconomic background than average Malaysians. This is not the exact representation of the entire population as the access to health providers, high quality food availability, health-supportive infrastructure and health knowledge levels are different in the urban as compared to the rural (41, 42). Hence, we are aiming for a better response in these areas due to a higher prevalence of MetS, absent of prevention measures and poor management among individuals with lower socioeconomic background (43). The applicability of peer support in these communities were shown to be well facilitated by the influence of lay health person, simplicity of health message, ability to collective set realistic health goals and the most important is that it is low in cost (43-45). Hence, it will be interesting to investigate responses from those with lower socio-economic status to a peer-led community health program. Eventually, PERSUADE can be an initiative peer support model to be implemented at the low socioeconomic community and suburban area for evaluation of its feasibility and cost-effectiveness. If successful, it can be a precursor for policy makers to initiate more rigorous promotion of such community peer-based programs to other parts of the country.

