		To identify and set a personal health goals	An infographic on healthy life style	To be able to set realistic health goals in term of body weight, waist circumference and weekly diet and physical activity planning

Table 3: PERSUADE outcome assessment

Outcome	Instrument
Socio-demographic information	A brief sociodemographic questionnaire is use to collect basic details (i.e. age, marital status, ethnicity, educational status, occupation, personal and household income, family size and number of years of residence in current location).
Lifestyle characteristics	A brief questionnaire will inquire on participants' smoking habit, alcohol consumption and sleeping pattern. A validated health-related quality of life (HRQOL) questionnaire will be used to determine subject's fulfilment of life.
Physical Activity	International Physical Activity Questionnaire (IPAQ) will be used to determine the level of physical activity of the participants.
Anthropometry	A height scale, body tape and bio-impedance machine will be used to measure participants' height, weight, waist and hip circumferences and body composition.
Nutrition and diet	A semi-food frequency questionnaire (SFFQ) and 3 days 24H food recall will be used to record the participants' nutrients and dietary intake.
Blood biomaker	Finger prick rapid method will be used to detect participants' fasting blood sugar levels and fasting lipid profile.

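### Allocation is by location among few neighbourhoods, and socioeconomic background is neither balanced across arms nor a planned covariate, although income and education are recorded

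*Combined protocol and SAP*

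**What the plan says.** **Unit of allocation.** Randomisation and Treatment Allocation states that "participants were randomised to either intervention or control group based on their location". Randomisation and Blinding repeats this: "as the randomisation will be made based on participants location, contamination of participants was minimised". Under Recruitment Process, screening and recruitment were "conducted in four low to middle income neighbourhoods". That these four neighbourhoods are the allocated locations is the natural reading, but it is an inference. The available text does not give the number of locations per arm.

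**Balancing.** "Eligible adults who have consented to participate are matched for age, sex and ethnicity as baseline". No socioeconomic factor is listed.

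**Analysis.** Statistical Analysis compares baseline characteristics by t-test or chi-square and analyses the outcomes by repeated-measures ANOVA over baseline, month 3 and month 6. It names no covariate and no location term.

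**Data available.** The sociodemographic row of Table 3 includes educational status and "personal and household income, family size". Other Measurements says these characteristics are recorded for all participants at baseline.

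**Why socioeconomic background matters here.** In the Discussion (Applicability in Low-to-middle Income Population) the authors write "we are aiming for a better response in these areas due to a higher prevalence of MetS". They add lack of prevention and poor management among people of lower socioeconomic background as further reasons.

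**The concern.** When whole locations go to one arm, any difference between those locations goes with them into the arm comparison. With hundreds of units such differences would tend to cancel; with about four they need not. Matching on age, sex and ethnicity does not equalise income or education. Analysing change within person does not help either if better-off and worse-off areas change at different rates over the six months.

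The protocol gives its own reason to take this factor seriously, and it collects the variables needed to act on it. The stated model leaves them out. A difference between arms in MetS components could therefore partly reflect who lives where, and the planned analysis has no step that would separate the two.

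**Working it through.** **1. The plan's own figure.** The sample size is 48 per group after 20% dropout, so 48 × 0.8 = 38.4, or 38 evaluable per arm. No SD is given, so 48 cannot be checked directly. With the two-sided normal formula n = 2(1.96 + 0.84)²SD²/δ² and n/(1 − 0.2), 48 is returned with an SD of about 2.33 mmol/L at δ = 1.5, or about 2.80 at δ = 1.8. Two-sided 5% is an assumption, since sidedness is not stated. The figure is not in dispute here and serves only as a yardstick.

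**2. Yardstick in SD units.** With 38 per arm, two-sided 5% and 80% power, the detectable difference is 0.65 SD by the t-test (0.651). The normal approximation gives 2.80 × √(2/38) = 0.643. Both treat participants as independent.

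**3. Illustration with income bands (assumed).** Suppose two neighbourhoods are lower-income, two are higher-income, and the split is 2:2. There are C(4,2) = 6 allocations, and 2 of them (33%) put both lower-income areas in one arm. In those two, arm and income band coincide. The last column gives the chance that a 5% t-test rejects when the intervention has no effect and such an allocation has been drawn, ignoring clustering.

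| Assumed difference in change between bands | Share of 0.651 SD | Rejection rate under no effect |
|---|---|---|
| 0.1 SD | 15% | 7% |
| 0.2 SD | 31% | 14% |
| 0.3 SD | 46% | 25% |

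**4. A second route, without bands (assumed).** Let ρ be the share of income variance lying between locations, with two locations of 24 per arm. The arm difference in mean income, in SD units, has standard deviation √(2[ρ/2 + (1 − ρ)/48]).

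| ρ | SD of arm difference | P(difference > 0.25 SD) | P(difference > 0.5 SD) |
|---|---|---|---|
| 0 (individual allocation) | 0.204 | 22% | 1% |
| 0.02 | 0.247 | 31% | 4% |
| 0.05 | 0.299 | 40% | 9% |
| 0.10 | 0.371 | 50% | 18% |
| 0.20 | 0.483 | 60% | 30% |

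If income correlates r with the outcome, the induced intracluster correlation is r²ρ and the design effect is 1 + 23r²ρ. Averaged over allocations, the type I error at a nominal 5% is 2[1 − Φ(1.96/√DE)]:
- ρ = 0.02, r = 0.2: DE 1.018, error 5.2%
- ρ = 0.10, r = 0.1: DE 1.023, error 5.3%
- ρ = 0.10, r = 0.3: DE 1.207, error 7.4%
- ρ = 0.20, r = 0.3: DE 1.414, error 9.9%

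**5. Comparison with clustering as a whole (assumed).** With 19 evaluable per location and an outcome intracluster correlation of 0.01 to 0.05, the design effect is 1 + 18 × ICC = 1.18 to 1.90. Type I error of an analysis that ignores location is then about 7% to 16%. By the normal approximation, power falls from 80% to about 73% to 53%. Income is one contributor to this larger effect.

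**The case against.** A reader might infer from the Discussion that the protocol itself says income drives response. It does not. The passage voices a hope for the study areas as a whole, names socioeconomic background rather than income, and treats response in this group as something still to be investigated. The sentence that "access to health providers, high quality food availability, health-supportive infrastructure and health knowledge levels are different in the urban as compared to the rural" is an urban-rural contrast, offered to explain why the sample does not represent the whole country. It is not a comparison among the four neighbourhoods.

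A reader might also infer that the neighbourhoods run from poor to middling. The phrase "four low to middle income neighbourhoods" is a label shared by all four, and screening took place around one district. No spread between them is documented, and the shared band limits how large it could be, although it does not balance the arms.

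The other side has further points that stand:
- If locations are truly randomised, the two extreme allocations are equally likely and opposite in sign, so the expected bias is zero. The problem is chance imbalance in the one allocation drawn, and the average error inflation may be small.
- The baseline comparison would reveal an arm-level imbalance.
- Adjusting for individual income and education does not remove area-level differences such as access to providers, food or infrastructure.
- Clustering matters more than income.

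These points limit the size of the concern and what the remedy can achieve, but they do not remove it. Showing an imbalance is not correcting it. A standard error that allows for clustering reflects the added uncertainty but does not undo an imbalance already drawn.

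**Conclusion.** The point holds in limited form. Allocation is by location, socioeconomic background is not among the matching factors, the outcome model names no covariate, and the relevant variables are collected. The trial therefore relies on chance among very few units to balance a factor that its own Discussion links to the hoped-for response.

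The size cannot be established from the documents. The 33%, and the 15% to 46% of the detectable difference, rest on an assumed 2:2 split, an assumed pattern of two lower- and two higher-income areas, and assumed differences of 0.1 to 0.3 SD. The 0.65 SD yardstick itself ignores clustering. On average over allocations, the type I error is about 5% to 10% across the values tried. The serious harm is confined to unlucky allocations. The documents do not show that the arms differ in income, or that income determines response.

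**What to change.** **Statistical Analysis.** Pre-specify baseline household income and education, together with the baseline value of the outcome, as covariates in the outcome model. If the baseline value enters as a covariate, the repeated responses should be months 3 and 6 only. If baseline stays among the responses, income and education need interactions with time, because a main effect alone would not adjust the comparison of change. Tabulate income and education by neighbourhood as well as by arm.

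**Randomisation and Treatment Allocation.** The protocol's tenses differ on whether allocation has been made. If it is not final, and the neighbourhoods do differ in income, restrict the random allocation so that each arm receives a lower- and a higher-income neighbourhood. Under the 2:2 pattern assumed above, this removes the 2 allocations in 6 that confound arm with income band. If allocation is done, only the analysis change applies.

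**State the limit.** Say in the plan that these steps do not remove other differences between locations, or the clustering created by allocating locations. Clustering needs its own handling in the sample size and the model.

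**Cost.** About one sentence in each section and no new data. The price is a few degrees of freedom at participant level and fewer possible allocations. Neighbourhood-level covariates would be far more expensive: with four locations in two arms, only about 2 degrees of freedom exist at that level.

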### *Control Group*

Participants in the control group will receive a one-time personalised nutrition and lifestyle advised based from the Malaysian Dietary Guideline 2010 (15). They will be assured to be followed up twice for the next six month. During this session, participants will be required to set realistic health goals particularly on their anthropometric measures, blood biomarkers, dietary practice and physical activity levels.

### *Intervention Group*

Participants residing in the location selected to be intervene will to form at minimum 4 peer groups. This group will receive a continuous three-months, peer-led nutrition and lifestyle behaviour intervention through a series of peer gathering. Two participants from each peer group will be selected as the peer leader (PL). PL will be trained to deliver the content of PERSUADE modules and will be responsible to run a weekly peer gathering with their respective groups for the following three months.

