## Study Sample

### Sample Size and Power Calculation

The estimated sample size based on earlier similar study (10) on one the study variables, fasting plasma glucose at 95% confidence and 80% power of an anticipated fall in FPG of 1.5 to 1.8 mmol/L. Using an equation to detect changes in a standard parallel-group trial and a 20% drop out rate, the calculated minimum required sample size is 48 participants for each group thus the totalling 96 for both randomized arm.

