### Peer Leader Selection

As an elaboration to the study flowchart (Figure 2), the intervention group will form a minimum number of eight peer groups with two PL will be selected from each group on voluntarily basis. PL will be trained for the all four modules and an extra module; health promotion. This module aimed at assessing appointed PL for leadership, health educator role, and understanding of the PERSUADE modules. All PL attended a two-days training session on focussing on leadership and communication skills. On top of that, a practical approach will be used, including physical, nutritional, and psychological aspects of a lifestyle change as included in all four PERSUADE modules. PL will be trained to engage with their peers in conversations about the issues of concern, seeking to promote health-enhancing knowledge and skills. The goal for each peer group is to be able to identify potential barriers and determinants of lifestyle improvement and subsequently take actions to reduce their CVD risk. At the end of PL training, a simple post-questionnaire will be distributed among them to indicate validity and adequateness of their knowledge and skills on all peer modules.

Respective PL will distribute the posters among their peer group every week to initiate discussion of relevant topics based on the weekly objectives. In order to maximise the participation, regular reminder about the next peer gathering sessions and short health message through text were regularly sent by PL. Peers will then have to keep the poster and returned it to the PL at the end of three months as a measure of compliance to the peer support program. Besides, peers are also encouraged to distribute the poster as a health promotion steps among the community.

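### Minimum number of peer groups is given as 4 and as eight, and under either number the planned ANOVA ignores peer-group clustering in the intervention arm

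*Combined protocol and SAP*

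**What the plan says.** On the number of groups, the Intervention Group section states: "Participants residing in the location selected to be intervene will to form at minimum 4 peer groups". The Peer Leader Selection section, which presents itself as an elaboration of Figure 2, states: "the intervention group will form a minimum number of eight peer groups with two PL will be selected from each group on voluntarily basis". Both sections take two leaders per group, and the leaders run weekly gatherings for three months.

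On the size of the arm, Sample Size and Power Calculation states: "the calculated minimum required sample size is 48 participants for each group thus the totalling 96 for both randomized arm". The method is described as "Using an equation to detect changes in a standard parallel-group trial and a 20% drop out rate". No allowance for clustering is mentioned.

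On location, Recruitment Process names four neighbourhoods, and Randomisation and Treatment Allocation assigns participants to arms by where they live. The text does not say how many neighbourhoods go to each arm.

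On analysis, the Statistical Analysis section applies a repeated-measures ANOVA at baseline, 3 months and 6 months to compare between and within the study groups. It names no term for peer group or location.

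**The concern.** Two minima that differ by a factor of two leave unclear how the intervention is to be delivered. Group size, the number of trained leaders and the number of clusters in the arm all follow from this figure.

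The analysis question arises whichever figure is meant. People who meet weekly under the same two leaders share a leader, a discussion and an attendance pattern, so their outcomes are likely to be correlated. A repeated-measures ANOVA allows for correlation between one person's visits. Without a further term it treats different people as independent. If the correlation within peer groups is positive, the standard error for the arm comparison is too small, the 95% intervals are too narrow and the p-values are too low. The control arm receives one-time individual advice and has no peer groups, so this clustering is in one arm only.

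**Working it through.** **The plan's own figure.** The 48 per arm cannot be reproduced because no standard deviation is given. Working back, 38/(1 − 0.20) = 47.5, rounded up to 48, and 40 × 1.2 = 48, so 38 to 40 evaluable per arm are implied. With two-sided alpha 0.05 (sidedness is not stated) and 80% power, SD = Δ√(n/2)/(1.96 + 0.84). This gives about 2.33 to 2.39 mmol/L for a fall of 1.5, and 2.80 to 2.87 for 1.8. Nothing below depends on this; 48 is taken as stated.

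**Inputs.** Arm size N = 48, a minimum (Sample Size and Power Calculation). Number of groups g = 4 (Intervention Group) or 8 (Peer Leader Selection). Two leaders per group (both sections). The documents give no intraclass correlation (ICC), so 0.02, 0.05 and 0.10 are assumed.

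**Group make-up.**
- g = 4: 48/4 = 12 per group; 2 × 4 = 8 leaders; 8/48 = 16.7%.
- g = 8: 48/8 = 6 per group; 2 × 8 = 16 leaders; 16/48 = 33.3%.

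**Clustering.** The intervention-arm design effect is DE = 1 + (m − 1) × ICC, with m the group size. With equal arms, equal variances and no peer-group clustering in controls, the variance of the between-arm difference is multiplied by (DE + 1)/2, and the standard error by the square root of that.

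| ICC | DE, 4 groups | SE factor, 4 groups | DE, 8 groups | SE factor, 8 groups |
|---|---|---|---|---|
| 0.02 | 1.22 | √1.110 = 1.05 | 1.10 | √1.050 = 1.02 |
| 0.05 | 1.55 | √1.275 = 1.13 | 1.25 | √1.125 = 1.06 |
| 0.10 | 2.10 | √1.550 = 1.24 | 1.50 | √1.250 = 1.12 |

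**What the discrepancy itself is worth.** The ratio of the two standard errors, 4 groups to 8, is √(1.110/1.050) = 1.03, √(1.275/1.125) = 1.06 and √(1.550/1.250) = 1.11. It therefore changes the standard error by about 3% to 11%.

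**After dropout.** If 20% leave evenly, 38.4 remain and groups average 9.6 or 4.8. For ICC 0.02, 0.05 and 0.10, DE is 1.172, 1.43 and 1.86 with 4 groups, and 1.076, 1.19 and 1.38 with 8. The SE factors become √1.086 = 1.04, √1.215 = 1.10 and √1.430 = 1.20 with 4 groups, and √1.038 = 1.02, √1.095 = 1.05 and √1.190 = 1.09 with 8. The problem shrinks somewhat but remains.

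**Degrees of freedom.** The between-group variance would rest on about 4 − 1 = 3 or 8 − 1 = 7 degrees of freedom, fewer if location is also modelled.

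**The case against.** The strongest reply is that the two sections need not conflict. One speaks of participants in the location chosen for intervention, the other of the whole intervention group. With four neighbourhoods and equal arms, two intervention locations with four groups each would give eight. Both figures are minima, so forming eight groups satisfies both. Figure 2, which Peer Leader Selection elaborates, is not shown and may settle the matter. This stands in part. A reader might infer a flat contradiction, and the documents do not establish one. Against the benign reading, the Intervention Group section refers to a single location, and the text never gives the number of locations per arm. A clarification is still needed.

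A reader might also infer that leaders distort the result, since they could be a third of the arm. The documents give no basis for any difference in response between leaders and other peers. Leaders are participants in the intervention arm and part of the programme, so including them does not bias the estimate of the programme's effect.

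A third tempting reading is that the trial loses a large share of its information. At ICC 0.05 the effective size of the intervention arm is 48/1.55 = 31 or 48/1.25 = 38, but that describes one arm. The between-arm standard error is the relevant quantity, and its inflation is smaller.

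Finally, it is fair to say that allocation by location is a separate and possibly larger clustering problem. Peer groups sit within allocated locations, so a peer-group term alone does not deal with it. That limits what this fix achieves but does not remove the need for it.

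**Conclusion.** The point holds in two parts of unequal weight. The differing minima are a minor inconsistency in the visible text: the sections must be reconciled, and the documents do not show which number is intended. The more important part is that the planned ANOVA leaves out peer-group clustering under either number, so for any positive ICC the planned intervals are too narrow. For ICC 0.02 to 0.10 the between-arm standard error should be larger by about 5% to 24% with 4 groups and 2% to 12% with eight.

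The direction is certain for a positive ICC; the size rests on the assumed ICC, enrolment at the minimum of 48, equal group sizes, equal arms and variances, and no peer-group clustering in controls. More participants or more groups would change the figures. A reader might take this as showing that 48 per arm is wrong; without a standard deviation that cannot be tested, and it is not claimed here.

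**What to change.** 1. Reconcile Intervention Group and Peer Leader Selection. State the minimum number of peer groups per intervention location and in total, and make the text agree with Figure 2.
2. Record a peer-group identifier for every intervention participant from the time the groups are formed.
3. Replace the repeated-measures ANOVA with a mixed model that has a peer-group random effect in the intervention arm only (partially nested), participant-level correlation across visits, and a small-sample degrees-of-freedom correction such as Satterthwaite or Kenward–Roger. Let the group effect act on the post-baseline values, for example with baseline as a covariate, because a group intercept shared with baseline would largely cancel from the change.
4. Specify this alongside whatever handling of location is adopted. The peer-group term does not cover allocation by location.
5. Keep all participants, leaders included, in the primary analysis. A summary of leaders and non-leaders is optional and descriptive only, since leaders are volunteers and number 8 to 16.

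The cost is a wording correction, one recorded variable and a respecified model, which is more than adding a term to the ANOVA. Intervals will be wider, appreciably so at the upper end of the ICC range. The between-group variance will be imprecise with 4 to 8 clusters.

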### Statistical Analysis

Diet and nutrition data will be analysed using Axxya Systems Nutritionist Pro™ Diet Analysis while all statistical analyses are performed with IBM® SPSS® Statistics 23.0. Descriptive methods will be used to demonstrate to describe participant characteristics and the consistency of both groups. Independent t-test or Chi Square will be used to evaluate baseline characteristics of peer intervention

participants compared to control, overall significance of improvement across clinical outcome measures. As this is a RCT involving repeated measures, the ANOVA repeated measures model is applied to observe significant differences between and within the study groups. This includes change in clinical measures of MetS component from baseline, end of trial (3rd month) and follow up (6th month). The magnitude of change in both primary and secondary outcome measures will be estimated and the given 95% confidence intervals with the p value 0.05 was taken as the level of significance.

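### The planned t-tests and repeated-measures ANOVA ignore correlation within intervention peer groups, so between-arm p values and 95% CIs are too optimistic if the peer-group ICC is positive

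*Combined protocol and SAP*

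**What the plan says.** All references are to the combined protocol and SAP.

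- **Delivery, intervention arm.** The Intervention Group section says that participants in the selected location "will to form at minimum 4 peer groups". Two members of each group become its leaders and run that group's weekly meetings for three months. The Peer Leader Selection section gives a different minimum: "the intervention group will form a minimum number of eight peer groups with two PL will be selected from each group".
- **Delivery, control arm.** "Participants in the control group will receive a one-time personalised nutrition and lifestyle advised". No control groups are described.
- **Allocation.** The Randomisation and Treatment Allocation section allocates by location. The Recruitment Process section names four neighbourhoods. The split between arms is not stated.
- **Analysis.** The Statistical Analysis section names the t-test and chi-square, and then says "the ANOVA repeated measures model is applied to observe significant differences between and within the study groups", with "95% confidence intervals with the p value 0.05 was taken as the level of significance". It contains no peer-group or location term, ICC, mixed model or robust variance.
- **Sample size.** The Sample Size and Power Calculation section works from "Using an equation to detect changes in a standard parallel-group trial and a 20% drop out rate", with no allowance for clustering.

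**The concern.** Members of one peer group share leaders, discussions, reminders and weekly contact for three months. The Outcome Assessment section also has trained leaders helping with the assessments. Shared influence is the intended mechanism, so some positive correlation of outcomes within a group is plausible. Nothing comparable acts among controls, so this layer of clustering exists in one arm only.

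A t-test or a between-arm ANOVA contrast treats participants as independent. It therefore omits the peer-group variance from the standard error. One or two well-led or badly led groups could then pass for a programme effect, with a false-positive rate above the stated 0.05 and intervals that cover less often than 95%.

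**Working it through.** **The plan's own figure.** The 48 per arm cannot be reproduced, because no SD is given. The dropout step is consistent: 38/(1 − 0.20) = 47.5, rounded up to 48 (or 40 × 1.2 = 48), and 2 × 48 = 96. With n = 2(1.96 + 0.8416)²(σ/δ)² and n = 38, the implied σ is 2.33 mmol/L for δ = 1.5, 2.80 for δ = 1.8, and 0.47 if the two values are read as differing by δ = 0.3.

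**Inputs.** From the documents: 48 enrolled per arm, 20% dropout (about 38 evaluable), 80% power, level 0.05, at least 4 or at least 8 groups. Assumed: a two-sided test, equal group sizes, equal total variance in the arms, no location effect (relaxed below), and a peer-group ICC ρ of 0.01, 0.05 or 0.10 for the quantity compared.

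**Formulas.** With m = participants per group:

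- design effect in the intervention arm: DE = 1 + (m − 1)ρ; in the control arm: 1
- variance inflation of the arm difference: V = (1 + DE)/2
- true type I error of the planned test: 2[1 − Φ(1.96/√V)]

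Example with 38 per arm, 4 groups and ρ = 0.05: m = 9.5, DE = 1 + 8.5 × 0.05 = 1.425, V = 1.2125, √V = 1.101, and 2[1 − Φ(1.780)] = 7.5%.

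| Per arm | Groups (m) | ρ = 0.01: V, error | ρ = 0.05: V, error | ρ = 0.10: V, error |
|---|---|---|---|---|
| 38 | 4 (9.5) | 1.043, 5.5% | 1.213, 7.5% | 1.425, 10.1% |
| 38 | 8 (4.75) | 1.019, 5.2% | 1.094, 6.1% | 1.188, 7.2% |
| 48 | 4 (12) | 1.055, 5.6% | 1.275, 8.3% | 1.550, 11.5% |
| 48 | 8 (6) | 1.025, 5.3% | 1.125, 6.5% | 1.250, 8.0% |

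At ρ = 0.05 with 38 per arm, the reported interval is too narrow by 1 − 1/√V: 9% with 4 groups and 4% with 8. With a correct standard error, power is Φ(2.8016/√V − 1.96), which is 72% and 76% in place of 80%.

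**Would a location term deal with it?** Simulated type I error, 20,000 trials per setting, 48 per arm, two locations per arm assumed, no location effect, at ρ = 0.05 / 0.10:

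| Analysis | 4 groups | 8 groups |
|---|---|---|
| No cluster term | 8.2% / 11.9% | 6.4% / 8.0% |
| Fixed location term | 8.3% / 12.2% | 6.4% / 8.0% |
| Location means, t on 2 df | 5.0% / 5.1% | 5.2% / 5.4% |

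A random location effect tested with Wald z gave about 6.8% / 9.8% with 4 groups. That is indicative only: it rests on roughly 380 fits per setting, many with convergence warnings. The same model on 2 df never rejected.

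**Would a peer-group term alone be enough?** Not if locations differ. At peer-group ICC 0.05, a peer-group analysis that ignores location rejects about 9% of the time at location ICC 0.02 (8.7% with 4 groups, 9.2% with 8). At location ICC 0.05 it rejects 12.6% and 15.3%. Location ICC 0.02 with no peer-group correlation already takes the analysis with no cluster term to about 10%.

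**The case against.** Four objections have force.

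**Location.** A reader might infer that the problem survives any location term. It does not. Peer groups sit inside locations, so their variance enters the location means, and a test on between-location degrees of freedom holds close to 5%. Inflation persists with a fixed term, or with a random one tested by z or on individual-level degrees of freedom. The Statistical Analysis section plans neither kind of location term, so this limits the scope of the point without rescuing the plan.

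**Which clustering matters more.** Both arms are clustered by allocation, so controls are not simply independent individuals. Location is probably the larger problem, and fixing peer groups alone would give false reassurance. This stands and shapes the fix.

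**Size.** No ICC is given. At 0.01 the effect is negligible, and figures based on all 48 enrolled overstate it if dropout reaches 20%. This also stands; the error rates are conditional and are not properties of the trial.

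**Number of groups.** A reader might take the two figures as a range from 4 to 8. They are two unreconciled minima. Four groups in each of two locations would satisfy both, and the larger 4-group error rates would then not apply, but the documents do not say so.

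A reader might also suppose that leaders work across several groups. The documents tie each leader to one group, so the correlation at issue is within a group.

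**Conclusion.** The point holds in a limited form. The planned between-arm tests ignore a layer of correlation that the intervention itself creates in one arm, so p values and intervals are too optimistic whenever the peer-group ICC is positive.

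Over assumed ICCs of 0.01 to 0.10, true type I error runs from 5.2% (8 groups, 38 per arm) to 11.5% (4 groups, 48 per arm). It is immaterial at the low end and matters from about 0.05 with 4 groups. These figures rest on the assumed ICC, equal group sizes and no location effect. The results on location analyses also assume two neighbourhoods per arm. This should be changed, but as part of an analysis that respects allocation by location.

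**What to change.** 1. Reconcile the minimum of 4 peer groups (Intervention Group) with the minimum of eight (Peer Leader Selection). State the number of locations per arm and of peer groups per location.
2. Record the peer-group ID of every intervention participant from the outset. If membership is not captured, the correction may be impossible later.
3. In the Statistical Analysis section, prespecify a mixed model that treats location as the allocation unit and adds a random peer-group effect in the intervention arm only. Give it arm-specific residual variance and Satterthwaite or Kenward-Roger degrees of freedom. State that the peer-group term is additional to the location-level allowance.
4. Report the peer-group and location ICCs, and add an assumed ICC range to the sample size section.

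**Cost.** The change itself is some SAP wording and one data field. The inferential cost is larger: wider intervals and few degrees of freedom, possibly about 2 for between-location inference, with very low power. For peer-group correlation alone at ICC 0.05, with group size held fixed, 80% power needs 38 × 1.2125 = 46.1, so 47 evaluable and 47/0.8 = 58.75, so 59 enrolled per arm with groups of 9.5 evaluable. With groups of 4.75 it needs 38 × 1.0938 = 41.6, so 42 evaluable and 42/0.8 = 52.5, so 53 enrolled. Both are lower bounds, because they use normal quantiles and allow nothing for location.
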